### 3.3. C. Research Design and Methods: R61 Phase.

**3.3. C.1. Overview.** The R61 Phase is designed to clarify engagement of the attention allocation target, to optimize dosage of GC-MRT (RCT comparing 8 vs. 12 sessions), and to explore whether the treatment engages two processes influencing attention allocation: disengagement from threat, and social reward.

**3.3. C.2. R61 Method: Patients:** The goal is to enroll a sample with clinically significant SAD, using few exclusion criteria to maximize generalizability. Patients will be obtained by clinical referral and recruitment notices posted online and locally. Forty adults age 18-60 with clinically significant SAD, as assessed by MINI structured interview and self-rated Liebowitz Social Anxiety Scale (LSAS-SR) total  $\geq 50$ , will enter the study after psychiatric clinical evaluation, including and Hamilton Rating Scale for Depression (HRSD). The LSAS cutoff score was chosen for optimal balance between diagnostic specificity and sensitivity for SAD. Key exclusion criteria will be at least moderately severe depression (HDRS 17-item score  $>20$ ), indicating greater need for non-experimental treatment; substance use disorder in the past 30 days (other than nicotine, or mild alcohol or cannabis abuse); bipolar or psychotic disorders; acute suicidal ideation (assessed by Columbia Suicide Severity Rating scale, CSSR); other unstable psychiatric, neurological, or medical conditions that could interfere with study participation or interpretation of outcomes; contraindication to MRI. (see Human Subjects for details).

[figure not shown]
The self-rated version of the LSAS will be used only at screening for eligibility assessment. The clinician-rated LSAS will be the primary outcome measure, assessed at baseline, during treatment, and post-treatment. Using the self-rated LSAS at screening avoids the bias that reportedly can occur when the primary outcome measure is the basis for an entry cutoff criterion, as raters could feel pressured to maximize baseline scores to meet the cutoff, thus distorting outcomes.

**3.3. C.3 R61 Intervention:** Patients will be randomized to 8 biweekly sessions of GC-MRT over 4 weeks vs. 12 sessions of GC-MRT over 8 weeks (8 biweekly, then 4 weekly), using GC-MRT as described above in the preliminary study, but without a control treatment – all R61 patients will receive active GC-MRT.

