### 3.3. C.5 Data Analysis and Hypothesis Testing

All quantitative measures will be graphed by group and checked for outliers and inconsistent values. If a variable has many outliers or shows heteroscedastic behavior (i.e., unequal variances), we shall consider transformations using a power function. Any remaining outliers will be winsorized (i.e., censored down to the nearest non-outlier value). Missing values. Missing values on outcome measures will be summarized by randomization group. We will test for differential missingness between groups. We will use mixed effect models for the statistical analyses, as these can analyze data with ignorable missingness (missing at random). G\*Power 3.1. and the R library longpower were used to calculate statistical power.

**R61.** Forty adults with SAD will be randomized to standard GC-MRT (8 sessions in 4 weeks) or extended GC-MRT (8 sessions in 12 weeks), with the target of attention allocation assessed at each session. **Aim 1:**

Hypothesis 1: *The target measure (% dwell time on threat faces) will decrease significantly during GC-MRT.*

The primary analysis will be intention-to-treat using a mixed effect model with change in % dwell time from baseline to the repeatedly measured outcome from all sessions after session 3 in both groups, using categorical time and baseline % dwell time as fixed effects, with an AR(1) correlation structure within subjects. The effect of interest will be the intercept, as this is a pooled analysis that does not differentiate between randomization groups or time points. A secondary analysis will use data from all sessions to test the categorical time effect predictor's effect, to identify time points with significant mean change scores adjusting for baseline medication use (yes/no). Additionally, the completer analysis will be a matched pair t-test of pre-post % dwell time values. Power Analysis: For the completer analysis, our already published data lead us to expect an effect size for reduction in the % dwell time of at least Cohen's  $d = 0.68$ . Assuming a 10% dropout with  $N=40$  enrolled subjects, and a 0.05 significance level, we will have at least 98% power to detect this change, with  $d = 0.48$  the minimum detectable effect size. For the repeated measures analysis, with within-subject autocorrelation parameter  $r = 0.6$ , we will have at least 80% power to detect an effect size of  $f = 0.17$ ,

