**R61 Go-Nogo Criterion:** Mean % dwell time on threat faces during the last session of the 8-session or 12-session treatment will decrease by more than 7.2 percentage points relative to baseline, corresponding to a medium effect size of Cohen's  $d=0.48$ , based on preliminary data. We have  $>80\%$  power to detect this difference under all scenarios. Clinical significance of cutoff: Based on preliminary data, since % dwell time reduction will partially mediate clinical symptom reduction, this effect corresponds to symptom reduction of  $d = 1.34$ , corresponding to 21.3 points on the LSAS scale. **R61 criterion for selecting dose for the R33:** If only one dosage group passes the Go-Nogo Criterion, that dose will be selected for the R33. If both dosage groups satisfy the Go-Nogo Criterion, we will decide based on the following: If improvement (decrease) in LSAS total score 8 weeks after starting treatment is at least 7 points greater in the 12-session/8-week treatment group than in the 8-session/ 4-week treatment group, we will use the 8-session/12-week treatment in the R33.

**Aim 4: Hypothesis 3:** *Compared to control treatment, GC-MRT will significantly improve symptoms (LSAS) & QoL (Quality of Life Enjoyment & Satisfaction Scale, QLESQ: a) at post-treatment and b) at 3-month follow-up.* As primary analysis, we will use a two-sample t-test for the LSAS change scores at the last session in completer subjects. For the 3-month follow-up, a similar analysis will be performed. Secondary analysis will be similar analyses of the QLESQ, and a mixed effects model of each outcome with change score (relative to baseline) as the outcome, and randomization group, time point, and the baseline score as the predictors. Power Analysis. We assume 10% drop-out in each group. From our preliminary data analysis, expected effect size for reduction in LSAS for completer subjects, compared to controls, will be  $d = 1.35$ . Using a two-sample t-test, with Bonferroni-corrected 0.025 significance level, we will have 99% power to detect this. We do not have preliminary data for the QLESQ; the minimal detectable effect size for the change difference will be  $d=0.74$ , a moderate effect size.

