**Hypothesis 4:** *After GC-MRT, change in % dwell time post-treatment will be significantly associated with improvement in LSAS and QLESQ totals at post-treatment and at 3-month follow-up.* We will calculate Pearson correlation coefficients between % dwell time reduction and LSAS reduction, and, separately, for % dwell time and QLESQ reductions. Power Analysis. From our preliminary data analysis, the expected correlation coefficient for the reduction in % dwell time and reduction in LSAS will be  $r > 0.32$ . With  $n = 80$  subjects and 10% dropout, we will have 80% power to detect a Pearson correlation of  $r = 0.32$  at the 0.05 level.

**Aim 5 (Exploratory):** *To assess whether attention control and reward processing predict symptom change (using same assessment methods as in Aim 3), with fMRI done pre- and post-treatment in a subset ( $n=60$ ).* We will fit regression models, with LSAS change relative to baseline as outcome, and with the baseline predictors listed above as fixed effects, Moderation relationships of treatment effect for the baseline predictors will be explored by including interaction terms with randomization group. We will test the association between change in attention control and reward processing and change in symptoms by Pearson correlation coefficients.

fMRI Data Acquisition: Prior to scanning, patients will practice all tasks and gain familiarity with the scanning environment. Foam pads securing patients in the head coil will limit head movement during data acquisition. The MRI component will last approximately one hour and 15 minutes, using a 3T General Electric MR750 (GE Medical Systems, Waukesha, WI, USA) located in NYSPI, and equipped with a 32 channel receive-only head coil. At the beginning of each session, 15 minutes resting state data will be collected to explore connectivity

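### No planned analysis compares % dwell time on threat between GC-MRT and control, so H1, H3 and H4 could all be met without a treatment effect on the named target

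*Combined protocol and SAP*

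**What the plan says.** All references are to section 3.3. C.5 (Data Analysis and Hypothesis Testing) of the combined protocol and SAP, unless stated otherwise.

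- **R61 design (3.3. C.3).** There is no control treatment: "all R61 patients will receive active GC-MRT". The randomised contrast is between two active schedules.
- **Hypothesis 1 (R61).** Of the primary mixed model the plan says: "The effect of interest will be the intercept, as this is a pooled analysis that does not differentiate between randomization groups or time points". In addition, "the completer analysis will be a matched pair t-test of pre-post % dwell time values".
- **Aim 2 (R61).** Dwell time at the last session is compared between the two dose groups, and no difference is expected.
- **Aim 3 (R61, exploratory).** Change in dwell time is correlated with task measures, and predictors of its reduction are explored.
- **R61 Go-Nogo Criterion.** The rule is a mean fall of more than 7.2 points from baseline. Its clinical meaning is argued from preliminary data, "since % dwell time reduction will partially mediate clinical symptom reduction".
- **Hypothesis 3 (R33).** "Compared to control treatment, GC-MRT will significantly improve symptoms (LSAS) & QoL". The between-arm tests cover LSAS and QLESQ.
- **Hypothesis 4 (R33).** "change in % dwell time post-treatment will be significantly associated with improvement in LSAS and QLESQ totals at post-treatment", tested by Pearson correlations and powered on n = 80 with 10% dropout.
- **Other R33 active-versus-control analyses.** These cover the EFSAT task (imaging and behaviour) and the reward task; the resting-state section also has a two-group connectivity comparison.

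**The concern.** Whether GC-MRT engages its target is a causal question: does dwell time on threat fall more with GC-MRT than it would without it? A before-and-after fall in treated patients does not separate the treatment from habituation to repeated face matrices or growing familiarity with the task. The baseline adds to this. Under 3.3. C.4.a it averages the first five matrices of Session 1, whereas each later session score averages 30.

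A correlation between dwell change and symptom change does not fill the gap. Patients who improve for any reason may look less at threatening faces, in either arm. If n = 80 is taken literally, the H4 correlation pools both arms and so mixes within-arm association with any difference between arms. In neither case does it show that treatment moved the target.

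Suppose dwell time fell equally in both R33 arms while LSAS improved more with GC-MRT. H1 could be significant, H3 could be significant and H4 could show a correlation, yet the treatment effect on attention would be zero. The LSAS comparison itself would be unaffected. What is at stake is the interpretation of how the treatment works.

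**Working it through.** **1. Every planned use of % dwell time, side by side**

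| Analysis | Phase | Control arm in a between-arm dwell test? |
|---|---|---|
| H1 mixed model and paired t-test | R61 | No; all patients active |
| Aim 2, dose groups at last session | R61 | No; both groups active |
| Aim 3 correlations and predictors | R61 | No |
| Go-Nogo, fall of more than 7.2 points | R61 | No |
| H4 correlations | R33 | No; association only |

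The R33 active-versus-control tests use LSAS, QLESQ, EFSAT and the reward task. EFSAT is not a substitute: it yields reaction times, accuracy and BOLD signal, whereas 3.3. C.4.a defines the target by eye-tracked dwell time.

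**2. The plan's own figures reproduce**

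Inputs from C.5: 40 enrolled in R61 and 10% dropout, so 40 × 0.9 = 36 completers; d = 0.68; alpha 0.05, taken as two-sided.

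- Paired t-test: noncentrality = d√n = 0.68 × √36 = 4.08 on 35 df. Power is 97.8% (plan: 98%). The effect detectable with 80% power is d = 0.48, as stated.
- H3: two-sample t-test, noncentrality = d√(n/2). With 36 per arm at alpha 0.025, 80% power is reached at d = 0.74, as stated. The plan does not give the R33 arm size here, but this match and 80 × 0.9 / 2 = 36 both support it.
- H4: n = 72, r = 0.32, Fisher z: atanh(0.32) × √69 − 1.96 = 0.79, so power is 78.7%. A noncentral-t approximation gives 80.7% (plan: 80%).

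The gap is therefore a missing analysis, not an arithmetic error.

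**3. What the uncontrolled test can pick up**

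The Go-Nogo figures imply a change SD of 7.2 / 0.48 = 15 points. The documents give no control-arm dwell change, so I assume a range of non-specific falls, with no GC-MRT-specific effect. These figures are for the 36-completer paired t-test, not the primary mixed model.

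| Non-specific fall | d | Paired test significant |
|---|---|---|
| 1.5 points | 0.1 | 9% |
| 3 points | 0.2 | 21% |
| 4.5 points | 0.3 | 42% |

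A between-arm test would stay at 5% in each row, because the fall is common to both arms.

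**4. Power of the missing R33 comparison**

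Unadjusted two-sample t-test on change, 36 completers per arm, SD 15 in both arms. The plan's d = 0.68 corresponds to 0.68 × 15 = 10.2 points.

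| Control-arm fall (assumed) | Between-arm d | Power at 0.05 | Power at 0.025 |
|---|---|---|---|
| 0 | 0.68 | 81% | 72% |
| 1.5 points | 0.58 | 68% | 57% |
| 3 points | 0.48 | 52% | 40% |
| 5.1 points (half) | 0.34 | 30% | 20% |

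The noncentrality in the first row is 0.68 × √18 = 2.88. The effect detectable with 80% power at 0.05 is d = 0.67, or about 10 points.

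**The case against.** **The document may not show everything.** It contains no separate R33 methods section, so the control procedure and the R33 assessment schedule cannot be seen. This stands as a limit: the finding covers the text available. But the R33 hypotheses and their analyses are set out in C.5, and this test is not among them.

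**A reader might infer that neither phase can show target engagement, or that R61 looks at dwell time only before and after.** The documents support neither reading. R33 is randomised against control and could show engagement if the comparison were analysed. R61 does compare dwell time between dose groups, though both are active.

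**Control-arm dwell data may not exist.** Section 3.3. C.4 promises the measurement at GC-MRT sessions, and H4 opens by referring to GC-MRT. Tracking of control sessions is inferred only from H4's n = 80. This stands, and it cuts both ways. If only the GC-MRT arm has dwell data, H4 rests on about 36 completers, with about 48–50% power for r = 0.32 instead of the stated 80%.

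**The plan does not overclaim.** H1 is already worded as a decrease during GC-MRT, the Go-Nogo rule is relative to baseline, and H4 claims an association. The mediation wording is used to calibrate the R61 cutoff from preliminary data. All of this is fair: H1 needs no rewording, and the text does not commit the sponsor to concluding mediation from H3 and H4. It does, however, leave the plan without the test on which any such conclusion would depend.

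**The power figures do not match an adjusted analysis.** Correct. The 81% is for an unadjusted completer t-test, and baseline adjustment may raise it. The plan also expects d of at least 0.68, so 81% is not a ceiling. In the other direction, an alpha of 0.025, as used for H3, lowers it to 72%.

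**Conclusion.** The point holds in limited form. In the available text, no planned analysis sets % dwell time under GC-MRT against control. Meeting H1, H3 and H4 together would not establish that the treatment moved its target. The primary LSAS comparison is not affected, and the omission lies in the analysis list rather than in the R33 design.

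The plan's 98% power concerns change from baseline and gives no assurance on the between-arm question. There, power is about 81% at two-sided 0.05 if the whole d = 0.68 is specific to GC-MRT, and about 52% if the specific part is d = 0.48. These figures assume 36 completers per arm, a change SD of 15 points in both arms and no covariate adjustment. The control-arm falls are assumed values, since the documents give none.

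**What to change.** 1. Add to Aim 4 a pre-specified comparison of % dwell time at the last session between GC-MRT and control, adjusted for baseline % dwell time and the medication stratum, in all randomised patients with dwell data. State its alpha and its place relative to the Bonferroni-corrected H3 tests.
2. State that H4 will be read as evidence of mechanism only if this comparison shows an effect. Say whether the H4 correlations use both arms or the GC-MRT arm alone.
3. Confirm that control sessions are eye-tracked and scored in the same way as GC-MRT sessions.
4. Report the power with its assumptions, as a range over the control-arm change, rather than carrying over the 98%.

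The cost is one extra analysis and a less favourable power statement. If control sessions are tracked, as n = 80 implies, no new patients, visits or procedures are needed. If they are not, tracking would have to be added and H4's power restated.

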**Attention control task:** The Emotional Faces Shifting Attention task (EFSAT) will be used to assess distraction of attention by threat faces. EFSAT stimuli are comprised of a trio of geometric shapes (circles, rectangles, triangles) alongside a trio of faces within the same field of view. For "Match Faces," participants select one of two bottom faces (neutral vs. emotional) matching the emotion of the top target face. "Match Shapes" will have similar instructions, to select one of two bottom shapes that matches the top shape. Face stimuli are from a validated stimulus set, the identities always differ, and equal numbers of male and female faces are presented. The paradigm comprises 36 blocks: 18 blocks of matching shapes interleaved with 18 blocks of matching emotional faces, counterbalanced across two runs. Each target face condition (angry, fear, happy) is presented for an entire block six times without repetition. Each 20s "task" block contains four sequential matching trials, 4s each, preceded by a 4s instruction image to either "Match Faces" (attend to faces) or "Match Shapes" (attend away from faces). Participants respond by pressing response buttons. Stimuli will be presented using presentation software (Neurobehavioral Systems).

**Social Incentive Delay task:** This social reward version of the Monetary Incentive Delay task was developed to assess social and monetary reward processing. We will use the social reward processing runs of this task. Participants are informed that pictures of neutral faces will be presented as rewards for successful trials. Each of 3 runs are "win versions" (i.e., faces can be won or not won, but cannot be lost). Trial "wins" result in the presentation of a static image of a face with a neutral expression (closed mouth images selected from the NimStim set of facial expressions). Runs begin with a 10s instructional screen.

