### 3.3. C.4.c. Behavioral Task Assessments

**Attention Control Task:** (see EFSAT 3.3. C.4.c. above) This will assess reaction times for matching shapes alongside happy versus angry distractors.

**Probabilistic Social Reward Learning Task:** This 25-min task is presented using E-Prime (version 1.1; Psychology Software Tools, Inc, Pittsburgh, PA). Subjects press a button to indicate whether a short (11.5 mm) or a long (13 mm) mouth appeared on a previously mouthless cartoon face. The task includes three blocks of 100 trials. Within each block, an equal number of short and long mouths appear for 100 ms each. The difference between mouth sizes as well as the duration of stimulus exposure is small, providing an ideal experimental setting for a response bias to develop without risk of inducing performance at chance level.

Using an asymmetric reinforcer ratio elicits a response bias. Correct identification of either the short or long mouth is rewarded (by a video clip of smiling actor with thumbs up sign) three times more frequently ("rich stimulus") than correct identification of the other mouth ("lean stimulus"). The reinforcement allocation and key presses are counterbalanced across subjects. In each block, only 40 correct trials (30 rich, 10 lean) are

rewarded, so each subject is exposed to the same reward ratio. Subjects are informed that the purpose of this task is to win as much money as possible, and that not all correct response will receive a reward feedback; but they will be unaware of the disproportionate reward for one of the stimuli.

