patterns within reward and attention control brain regions. We will acquire functional T2\*-weighted echo-planar images (EPIs) depicting the blood-oxygen-level-dependent (BOLD) contrast (Repetition time: 2300 ms, echo time: 23 ms, flip angle: 90°). Whole brain acquisitions will consist of 30 sagittally oriented slices of 3.5mm thickness and 1.7x1.7mm^2 in-plane resolution (matrix: 128x128, field of view: 22 cm). The first six EPI volumes in each run will be discarded to avoid T1 equilibrium effects. High-resolution T1-weighted magnetization prepared rapid acquisition gradient-echo sequence will be obtained to serve as anatomical reference.

**fMRI Data Preprocessing:** Statistical Parametric Mapping (SPM12) software package (Wellcome Trust Centre for Neuroimaging, London; [www.fil.ion.ucl.ac.uk/spm](http://www.fil.ion.ucl.ac.uk/spm)) will be used for image processing steps. During preprocessing, images will be temporally corrected to account for differences in slice time collection, spatially realigned to the first image of the first run, normalized to a Montreal Neurological Institute (MNI) template, and smoothed with an 8 mm isotropic Gaussian kernel. Additionally, subjects with more than 3mm of head motion in any dimension from one EPI brain volume to the next will be removed from analysis.

**Attention Control Task fMRI:** Blocks of Match Faces (shapes in background) and Match Shapes (faces in background) will be modeled with 6 box-car regressors separately based on target emotion or shape (angry, fearful, or happy/ circle, square, or triangle), and effects will be estimated at each voxel for each participant and taken to the second level for random effects analysis. In addition, six movement parameters obtained during realignment will be included in the model as regressors to account for motion-related effects in BOLD signal.

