Whole-brain 2X2 voxel-wise Analysis of Variance (ANOVA) will be conducted to evaluate main effects of Time (pre- and post- treatment), Stimuli type (match faces and match shapes), and Time by Emotion interactions for only angry faces at the R61 phase for each dose group. For the R33 phase, whole-brain 2X2X2 ANOVA will be conducted to evaluate main effects of Group (active and control), Time (pre- and post-treatment), and Stimuli type (match faces and match shapes), and Group by Time by Stimuli type interactions for only angry faces. A stringent threshold for significance will be set at  $p < 0.05$ , corrected for multiple comparisons across the entire brain using a FWE with a cluster size of at least 10 contiguous voxels. Significant main effects and interactions will be tested by post hoc t-tests to clarify the direction of effects.

**Reward Task fMRI:** During individual-level analyses, functional activation maps of the reward task will be computed by regressing each voxel's fMRI response time course onto an ideal response function consisting of a canonical hemodynamic response function convolved with the time-series of each response type of the entire duration of anticipation and outcome phases of the task. In addition, six movement parameters obtained during realignment were included in the model as regressors to account for motion-related effects in BOLD signal.

A whole-brain voxel-wise two-way t-test model will be conducted with two time points (pre-, post-treatment) in the R61 phase for each dose group. It will be applied separately for the anticipatory and outcome phases of the task, and each outcome will be modeled against an implicit baseline (the anticipatory phase models only 'potential win' trials and the outcome phase models only successful 'potential win' trials). For the R33 phase, whole-brain 2X2 ANOVA will be conducted to evaluate main effects of Group (active and control), and Time (pre- and post- treatment), and Group by Time interactions. Significant clusters will be further evaluated by extracting subject- and condition-specific signal intensity coefficients to evaluate simple effects.

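### The EFSAT fMRI model codes Match Shapes blocks by shape, so the planned angry-only ANOVAs have no Match Shapes estimate specific to angry distractors

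*Combined protocol and SAP*

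**What the plan says.** All references are to the combined protocol and SAP.

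- **Task layout (3.3. C.4.b, fMRI Tasks).** "The paradigm comprises 36 blocks: 18 blocks of matching shapes interleaved with 18 blocks of matching emotional faces, counterbalanced across two runs". Each target emotion (angry, fear, happy) fills six whole blocks. The section gives the task's purpose as measuring how far threatening faces draw attention away.
- **Behavioural use of the same task (3.3. C.4.c).** Reaction times are taken for "matching shapes alongside happy versus angry distractors".
- **First-level fMRI model (3.3. C.5, Attention Control Task fMRI).** "Blocks of Match Faces (shapes in background) and Match Shapes (faces in background") are the two block types. They "will be modeled with 6 box-car regressors separately based on target emotion or shape", with the levels given as "angry, fearful, or happy/ circle, square, or triangle".
- **Second-level model, R61 (same paragraph).** A 2x2 whole-brain ANOVA evaluates Time, "Stimuli type (match faces and match shapes), and Time by Emotion interactions for only angry faces at the R61 phase for each dose group".
- **Second-level model, R33.** A 2x2x2 ANOVA adds Group and evaluates "Group by Time by Stimuli type interactions for only angry faces".

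The change measures for attention control feed Aims 3 and 5, both labelled exploratory.

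**The concern.** In a Match Shapes block the target is a shape and the faces are background. Coding by target therefore sorts these blocks by circle, square or triangle and ignores the emotion of the distracting faces. The second-level models keep angry faces only and use Match Shapes as one of the two Stimuli-type levels. An angry-specific version of that level needs a first-level estimate for shape matching beside angry faces, and none is defined.

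That condition is also the one the task exists to measure: the participant is told to attend to shapes while a threatening face competes for attention. If the analyst fills the gap with whatever Match Shapes estimates exist, the comparison changes task and emotion mix together. A pre-post change, or a group difference in that change, could not then be attributed to distraction by threat. The choice of substitute would also be made after the data are in, for whole-brain tests in both phases.

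**Working it through.** **1. Reproduce the plan's count.** Section 3.3. C.4.b gives 18 + 18 = 36 blocks, and 18 / 3 = 6 blocks per target emotion, as stated. The six regressors in 3.3. C.5 are 3 target emotions + 3 target shapes = 6. The figure reproduces.

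**2. Compare regressors with the cells needed.**

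| Cell for the angry-only ANOVA (each time point) | First-level regressor available |
|---|---|
| Match Faces, angry target | Yes: the angry regressor |
| Match Shapes, angry distractor | None: only circle, square, triangle |

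**3. Check estimability.** The documents do not allocate distractor emotion to the Match Shapes blocks, so a layout must be assumed. I used a 36-row block design matrix and asked whether the indicator for Match Shapes blocks with angry distractors lies in its column space.

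- *Crossed layout* (assumption: two blocks for each of the 3 x 3 shape-emotion pairs, 2 x 9 = 18). The written model has rank 6, and the indicator is not in its span. The angry-distractor effect is not estimable.
- *Fully paired layout* (assumption: each shape always appears with one emotion). The indicator is in the span, but shape and emotion are then completely confounded.
- *Coding both tasks by face emotion* (2 tasks x 3 emotions = 6 columns) in the crossed layout. The rank is 6 and the indicator is in the span. A simulated unit response in angry-distractor blocks returns 1.0 on that regressor and 0 on the other five.

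**4. What the pooled substitute estimates.** Let A, F and H be the responses to Match Shapes blocks with angry, fearful and happy distractors. In the crossed layout each shape regressor estimates (A + F + H) / 3, and so does their average. The pooled cell differs from the intended one by

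(A + F + H) / 3 - A = (F + H - 2A) / 3.

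- A = 1, F = H = 0: pooled value 1/3 (the least-squares fit gives 0.33 on each shape regressor).
- A = F = 1, H = 0: pooled value 2/3.
- A = F = H = 1: pooled value 1, no distortion.

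So the error depends on how the brain responds to the other two emotions as well as on the unstated allocation. Within one group the Time by Stimuli type interaction carries the pre-post change in this quantity. The R33 three-way interaction carries the group difference in that change.

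**5. Internal wording.** The R61 sentence names "Time by Emotion interactions for only angry faces at the R61 phase for each dose group". With one emotion retained, Emotion has a single level and cannot interact with Time. The two factors named in that 2x2 are Time and Stimuli type, and the parallel R33 sentence uses Stimuli type in its interaction.

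**The case against.** The strongest reply is that the planned ANOVA can be run. The restriction to angry faces may mean the angry Match Faces estimate set against all Match Shapes estimates, which fills every cell of both designs. That is correct, so a reader who infers that the analysis is impossible goes too far. What remains is that the Match Shapes cell would not be angry-specific, so the analysis would not match the stated purpose of the task.

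A second reply is that this may be a drafting slip. Two tasks by three emotions also makes six regressors, and the task description and behavioural section suggest that distractor emotion was the intended factor. This is plausible, but the text lists circle, square and triangle explicitly, so it needs correcting in either case.

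A third reply concerns size. A reader might infer that the threat effect is cut to one third. The documents do not support that as a general figure. They give no block count per shape and no allocation of distractor emotion, and the one-third value also needs zero response to fearful and happy distractors. It would apply to the Match Shapes cell alone, since the angry Match Faces estimate is intact.

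Finally, the aims are exploratory, and attention control is also measured by reaction times, which can be sorted by distractor emotion whatever the imaging regressors are. This limits the reach of the point but does not remove it.

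**Conclusion.** The concern holds for the EFSAT fMRI analysis. As written, the first-level model supplies no Match Shapes estimate specific to angry distractors, unless every shape is tied to one emotion. With pooled Match Shapes estimates, the Stimuli-type effect and its interactions with Time and Group mix task with emotion.

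The size is unknown. Under an assumed balanced layout the pooled cell departs from the intended one by (F + H - 2A) / 3, which is zero if all three emotions evoke the same response.

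It would be wrong to infer that Aims 3 and 5 as a whole fail. They also draw on the reward measures and on behavioural EFSAT data, which this does not touch. Nor are the dwell-time primary outcome, the Go-Nogo criterion, dose selection or the LSAS analyses affected. This is a specification error in an exploratory analysis, worth correcting before the imaging data are modelled.

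**What to change.** - Define the three Match Shapes regressors by the emotion of the background faces (angry, fearful, happy). The total stays at six.
- Use the angry Match Shapes estimate as the Match Shapes level in the R61 2x2 and R33 2x2x2 models.
- State how distractor emotion is allocated to the 18 Match Shapes blocks. The task description says emotion is constant within a block only for target faces. If distractor emotion varies within Match Shapes blocks, code it by trial instead of by block.
- In the R61 model, replace the Time by Emotion interaction with Time by Stimuli type.

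The cost is recoded onsets, re-run first-level models if any have been fitted, and a wording change in the SAP. No new data are needed, and block-level coding adds no regressors. What is given up is the separation of Match Shapes blocks by shape, which none of the planned second-level comparisons uses.
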